5.2 EXCLUSION CRITERIA

An individual who meets any of the following criteria will be excluded from participation in this study:

1. Experienced a Grade 4 systemic allergic reaction (per CoFAR Grading Scale for Systemic Allergic Reactions Version 3.0) to the first dose of the Pfizer-BioNTech or Moderna COVID-19 vaccine.
2. Known exposure to SARS-CoV-2 and still within the quarantine window.
3. Symptoms consistent with acute COVID-19 infection or known COVID-19 infection (positive reverse transcription-polymerase chain reaction [RT-PCR] or antigen test) and still within the quarantine window
4. Have an acute illness, including body temperature greater than 100.4 degrees F, within 14 days prior to enrollment.
5. History of autoimmune or other disorders requiring systemic immune modulators.
6. Are moderately or severely immunocompromised.
7. History of acute urticaria within 28 days prior to enrollment.
8. Pregnant.
9. Have received any vaccines within 14 days prior to enrollment.
10. Scheduled or planned receipt of approved or experimental vaccine prior to visit 3.
11. Had any allergen immunotherapy administration within 24 hours prior to the first study vaccination or plan to receive within 24 hours after the second study vaccination.
12. Have received a biological therapy within 6 months prior to enrollment.
13. Use of systemic steroids for any reason within 28 days prior to enrollment.
14. Use of zileuton within 14 days prior to enrollment.
15. Use of EUA monoclonal antibodies casirivimab and indevimab, or bamlanivimab, or any other antibody agent for treatment or prevention of COVID-19 within 3 months of randomization.
16. Presence of condition(s) that, in the judgment of the investigator or the referring physician, may put the participant at undue risk or make them unsuitable for participation in the study.

5.2.1 Exclusion of Special Populations

Children, adults who lack capacity to consent, and pregnant women: We are able to obtain knowledge about allergic responses to the mRNA COVID-19 vaccines without exposing children under age 16 (even though the Pfizer-BioNTech vaccine is authorized for emergency use in individuals 5 to 15 years of age, and authorizations for lower ages are anticipated), adults who lack capacity to consent, and pregnant women to the potential risk of severe allergic reactions.

5.3 INCLUSION OF VULNERABLE PARTICIPANTS

5.3.1 Participation of Children

Currently, the Pfizer-BioNTech vaccine is the only vaccine approved for use in children 16 to 17 years of age. They have no options for seeking another type of vaccine for full vaccination (unlike adults who can receive a non-mRNA vaccine), so there is an urgent public health need to determine the safety of giving a second dose in this population in order for them to be fully protected against COVID-19. Furthermore, there is likely to be significant hesitancy for practicing allergists to give a second dose to children who have had an anaphylactic reaction to the first dose unless evidence can be generated to support that it is safe to do so.

5.3.2 Adult Subjects Who Lack Capacity to Consent to Research Participation

Individuals who are unable to provide initial informed consent are excluded from the study. If participants lose the ability to provide ongoing consent subsequent to giving initial consent, they will be withdrawn from the study.

5.3.3 Participation of NIH Staff or Family Members of Study Team Members

NIH staff and family members of study team members may be enrolled in this study as this population meets the study entry criteria. Neither participation nor refusal to participate as a subject in the research will have an effect, either beneficial or adverse, on the participant's employment or position at NIH.

Every effort will be made to protect participant information, but such information may be available in medical records and may be available to authorized users outside of the study team in both an identifiable and unidentifiable manner.

The NIH investigator will provide and request that the NIH staff member review the Frequently Asked Questions (FAQs) for Staff Who are Considering Participation in NIH Research and the Leave Policy for NIH Employees Participating in NIH Medical Research Studies (NIH Policy Manual 2300-630-3). Please see section [10.1.3](#) for consent of NIH staff.

5.4 INCLUSION OF PREGNANT WOMEN, FETUSES OR NEONATES

Not applicable

5.5 LIFESTYLE CONSIDERATIONS

During this study, participants are asked to:

- Discontinue any medication (e.g., oral antihistamines) that might interfere with the vaccine challenge procedure, skin testing, or booster administration (as applicable) within an appropriate timeframe prior to the target procedure, depending on the medication.
- Refrain from taking multivitamins or supplements containing biotin (vitamin B7, which is commonly found in hair, skin, and nail supplements and multivitamins) for 12 hours before Visits 1, 3, 4, and 6.

5.6 SCREEN FAILURES

Screen failures are defined as participants who consent to participate in the clinical trial but are not subsequently assigned to the study intervention or entered in the study. A minimal set of screen failure information is required to ensure transparent reporting of screen failure

participants, to meet the Consolidated Standards of Reporting Trials (CONSORT) publishing requirements and to respond to queries from regulatory authorities. Minimal information includes demography, screen failure details, eligibility criteria, and any serious adverse event (SAE).

Individuals who do not meet the criteria for participation in this trial (screen failure) because of a modifiable factor may be rescreened. Rescreened participants should be assigned the same participant number as for the initial screening.

5.7 STRATEGIES FOR RECRUITMENT AND RETENTION

Participants will be recruited from referrals from outside physicians and from investigators or employees in the NIH Clinical Center. Letters and/or emails may be sent to physicians, allergists/immunologists, and other specialists, as well as directly to potential participants for subject recruitment. Fliers and other written information may be posted on the NIH campus, in newspapers and on news sites, and in public spaces including, but not limited to, libraries, listservs, and community events, advertising the study. Foundations and other patient advocacy groups may be contacted. The NIH media office may be contacted to issue a press release regarding the study. The study will be listed on clinicaltrials.gov. Information about the study may also be placed on social media sites.

5.7.1 Costs

No cost to participants is expected.

5.7.2 Compensation

Participant travel will be paid directly or reimbursed, per NIAID policy. However, participants will also be reimbursed for travel for their first in-person visit to the NIH (which would typically not be reimbursed per policy).

Participants will be compensated for study events and procedures after screening as summarized below:

Inpatient stay Day 0: \$350

Inpatient stay Day 1: \$350

Inpatient stay Day 2: \$350

Inpatient stay Day 3: \$300

Additional stay in ICU (e.g., if longer stay is needed to treat allergic reaction/AE): \$300/day

Additional stay on ward (e.g., if longer stay is needed to treat allergic reaction/AE): \$250/day

Blood draw (completion of all required per study team for study visit 1): \$150

Nasal swab: \$25

Urine collection (completion of all required for study visit 1): \$25

Outpatient follow-up visit: \$200

Outpatient blood draw: \$50 (\$150 at visit 4 only for participants who receive booster vaccination)

Outpatient skin testing: \$75

Visits 2 and 5 (as applicable) phone call/videoconference: \$20 each

Mental health/anxiety questionnaires: \$10 for each timepoint. Questionnaires completed during screening/enrollment and visit 1 (day 0) will be compensated \$10 total at the completion of visit 1. Participants must complete all questionnaires for the corresponding timepoint to receive the questionnaire compensation for that timepoint.

Psychiatric consultation (via telehealth appointment): \$20

The total maximum compensation for the required study visits and procedures as scheduled is \$2,195; however, compensation may be more than this if the participant receives a booster vaccination or if additional inpatient days or additional procedures are required. Screening procedures are not compensated. Subjects will receive remuneration after visit 2 (for visits 1 and 2) and after visit 4 or 6 (for visits 3, 4, 5, and 6, as applicable).

6 STUDY INTERVENTIONS

6.1 STUDY INTERVENTIONS ADMINISTRATION

6.1.1 Study Intervention Description

The Pfizer-BioNTech monovalent COVID-19 vaccine (Comirnaty) is approved by the FDA in individuals 12 years of age and older for active immunization to prevent COVID-19 caused by SARS-CoV-2. It is also authorized for use under EUA in additional populations, as described above (section 2.2). The bivalent formulation (Original and Omicron BA.4/BA.5) is authorized for use under EUA as a single booster dose for individuals 12 years of age and older who are at least 2 months removed from the completion of their completed primary vaccination or have received the most recent booster dose with any authorized or approved monovalent COVID-19 vaccine. The active ingredient in both formulations is nucleoside-modified mRNA encoding the SARS-CoV-2 spike protein. Additional details regarding the vaccine are provided below and in the prescribing information documents.[28, 29]

Commercially available sterile, preservative-free 0.9% Sodium Chloride Injection, USP will be used as placebo.

6.1.2 Dosing and Administration

A single dose of the Pfizer-BioNTech vaccines is 0.3 mL. Each dose of the placebo vaccine will match this volume (0.3 mL). All study vaccines will be administered intramuscularly in the deltoid in the order determined by the randomization schedule; the first and second vaccinations will be in opposite arms.

6.1.3 Booster Vaccination

Participants who receive a booster vaccination at visit 4 will receive a standard dose of the monovalent or bivalent Pfizer-BioNTech vaccine according to availability and participant choice.

6.2 PREPARATION/HANDLING/STORAGE/ACCOUNTABILITY

6.2.1 Acquisition and Accountability

The study drug will be distributed and accounted for by the NIH pharmacy according to standard pharmacy procedures.

6.2.2 Formulation, Appearance, Packaging, and Labeling

The Pfizer-BioNTech COVID-19 vaccines are supplied as frozen suspensions in vials with gray caps and labels with gray borders, and are not diluted prior to use. The label on the vials of the bivalent formulations are marked with the word “Bivalent.” Each dose contains 30 mcg of a modified messenger RNA (modRNA) encoding the viral spike (S) glycoprotein of SARS-CoV-2. Each dose of the Pfizer-BioNTech COVID-19 vaccines also includes the following ingredients: lipids (0.43 mg ((4-hydroxybutyl)azanediyl)bis(hexane-6,1-diyl)bis(2-hexyldecanoate), 0.05 mg 2-[PEG-2000]-N,N-ditetradecylacetamide, 0.09 mg 1,2-distearoyl-sn-glycero-3-phosphocholine, and 0.19 mg cholesterol), 0.06 mg tromethamine, 0.4 mg tromethamine hydrochloride, and 31 mg sucrose. The Pfizer-BioNTech COVID-19 vaccines do not contain preservative. The vial stoppers are not made with natural rubber latex.

The Pfizer-BioNTech vaccines will be labeled per pharmacy procedures and in accordance with regulatory requirements.

Each mL of placebo vaccine contains sodium chloride 9 mg and water for injection, quantity sufficient. It contains no bacteriostat, antimicrobial agent, or added buffer. The solution may contain hydrochloric acid and/or sodium hydroxide for pH adjustment.

6.2.3 Product Storage and Stability

Pfizer-BioNTech COVID-19 vaccine will be supplied in cartons in thermal containers with dry ice. Once received, the vial cartons may be stored in an ultra-low temperature freezer between -90°C to -60°C (-130°F to -76°F) or immediately transferred to the refrigerator [2°C to 8°C (35°F to 46°F)], thawed, and stored for up to 10 weeks. The 10-week refrigerated expiry date should be recorded on the carton at the time of transfer. Once vials are thawed, they should not be refrozen. If cartons are received at 2°C to 8°C, they should be stored at 2°C to 8°C. The carton should be checked to ensure it has been updated to reflect the 10-week refrigerated expiry date. During storage, minimize exposure to room light, and avoid exposure to direct sunlight and ultraviolet light.

If not previously thawed at 2°C to 8°C (35°F to 46°F), vials should be thawed at room temperature [up to 25°C (77°F)] for 30 minutes prior to use. Vials may be stored at room temperature [8°C to 25°C (46°F to 77°F)] for a total of 12 hours prior to the first puncture. After first puncture, the vial should be held between 2°C to 25°C (35°F to 77°F). Vials should be discarded 12 hours after first puncture.

Placebo should be stored at 20° C to 25°C (68° F to 77° F).

6.2.4 Preparation

The Pfizer-BioNTech COVID-19 vaccines are supplied as a frozen suspension that does not contain preservative. Each vial must be thawed prior to administration, and must not be diluted.

Detailed preparation instructions are provided in the full prescribing information documents.[\[28, 29\]](#)

The placebo vaccine will be prepared according to standard pharmacy procedures.

6.3 MEASURES TO MINIMIZE BIAS: RANDOMIZATION AND BLINDING

Participants will be randomized to receive either Pfizer-BioNTech vaccine or placebo on Day 1 in a 1:1 ratio at enrollment via block randomization. On Day 2, subjects will receive whichever of vaccine or placebo that was not given on Day 1. A randomization scheme will be generated by the NIAID Biostatistics Research Branch who will provide a randomized list of arm assignments to the NIH Clinical Center Pharmacy. The randomization code list will be maintained by the Investigational Drug Control Unit (IDCU) in the electronic Investigational Drug Management System (IDMS).

The participants, the clinical staff, and the study team will be blinded to the order of study vaccine assignments. The unblinded pharmacy staff is responsible for maintaining security of the assignments.

Intentional unblinding: Unblinding will occur after the last participant has completed Visit 1. There will be no emergency unblinding for CoFAR Grade 3 or lower reactions because allergic and anaphylactic reactions to the vaccine are expected and will be treated per standard clinical care, and it is not necessary to unblind to do so. However, if a CoFAR Grade 4 or higher systemic allergic reaction or other life-threatening AE occurs, then both the investigator and the participant will be unblinded. If a CoFAR Grade 4 or higher reaction occurs on day 1, then the participant will not receive the study intervention the next day (either placebo or vaccine).

To break a treatment blind, the principal investigator will request a participant's treatment assignment from the IDCU. If an emergency request for treatment assignment is made by an individual other than the principal investigator and the principal investigator is not immediately available, the request will be made to one of the physician associate investigators, who will then contact the IDCU or appropriate NIH pharmacy after-hours contact to obtain the treatment assignment. If a participant's study agent assignment is unblinded, the information will be provided to only the individuals needing it for treatment decisions; all attempts will be made to maintain the blind of the study team.

Unintentional unblinding: If the blind is unintentionally broken during the challenge, the study will proceed as normal, and the principal investigator will create a plan for preventing the recurrence of a similar incident, as appropriate. Since the active vaccine is known to have adverse side effects (e.g. fatigue, headache, fever, etc) based on data from the Phase 3 trials, patients who experience these symptoms may be unintentionally unblinded. However, if the participant experiences these symptoms on Day 2 (e.g. after receiving vaccine on Day 1), they may still receive the study vaccine on Day 2 without intentionally breaking the blind. Although these symptoms may indicate the participant received the active vaccine, this cannot be absolutely confirmed without direct knowledge of the participant's assignment; therefore, these instances will be evaluated by the principal investigator (without purposefully breaking the blind unless necessary) and will only be reported as outlined below if the assignment has been definitively revealed.

Intentional and unintentional unscheduled unblinding will be documented in the appropriate source and/or research record and will include the reason for the unscheduled unblinding, the date it occurred, who approved the unblinding, who was unblinded, who was notified of the unblinding, and the plan for the participant. The principal investigator will report all cases of intentional and unintentional unscheduled unblinding to the data and safety monitoring board (DSMB) in writing within 1 business day after site awareness via email to the DSMB mailbox ([contact]) outlining the reason for the unblinding and the date it occurred. The report will also be submitted to the sponsor medical monitor. If the unblinding meets the definition of a reportable event, it will be reported to the IRB according to NIH Human Research Protections Program (HRPP) Policy 801.

If an SAE has resulted in unblinding, this information will be included in the SAE report.

6.4 STUDY INTERVENTION COMPLIANCE

Participants in this study will receive the full dose of the assigned vaccine/placebo under direct observation.

6.5 CONCOMITANT THERAPY

The following medications are prohibited during participation in the study:

- Systemic immunomodulators including systemic steroids.
- Biologic agents that will interfere with the study objectives at the discretion of the investigator.
- EUA monoclonal antibodies casirivimab and indevimab, or bamlanivimab, or any COVID-19-specific biologic including antibodies or immunomodulator for at least 5 half-lives.
- Zileuton.
- Any investigational or approved vaccines administered outside of the study prior to visit 3 and, for participants receiving a booster vaccination at visit 4, at least 2 months before visit 4 through visit 6.
- Any allergen immunotherapy administration within 24 hours prior to the first study vaccination through 24 hours after the second study vaccination, and from 24 hours prior to through 24 hours after visit 4 (for participants receiving the booster vaccination).

Since one of the goals of this study is to understand the mechanisms of allergic reactions to the COVID-19 vaccines, these medications have been excluded since they may interfere with analysis in mechanistic studies.

Participants may be asked to discontinue use of antihistamines and drugs with antihistamine properties prior to the study intervention as well as prior to skin testing at visit 3 or 4 and booster vaccination at Visit 4 (as applicable) since these medications can mask signs and symptoms of an allergic reaction, thereby reducing the accuracy of skin testing and affecting results of research tests following the booster vaccination. Participants will be asked to discontinue these medications for a time period equal to at least 5 half-lives of the medication prior to the study

intervention.^[31] These medications can be resumed once the participant is discharged at the end of Visit 1 and after Visit 3 or 4.

Unless medically contraindicated, participants may also be asked to discontinue use of beta blockers, ACE inhibitors, and NSAIDS that are thought to interfere with treatment of allergic reactions or that may act as eliciting factors that increase reactivity in susceptible individuals^[31] for a time period of 5 half-lives of the medication prior to the vaccine challenge at Visit 1 and the booster vaccination at Visit 4 (as applicable). They can resume these medications once they complete the study interventions at the respective visit.

7 STUDY INTERVENTION DISCONTINUATION AND PARTICIPANT DISCONTINUATION/WITHDRAWAL

7.1 DISCONTINUATION OF STUDY INTERVENTION

Study intervention may be discontinued for an individual participant (i.e., pausing), or it may be discontinued for all participants and enrollment suspended (i.e., halting). Pausing and halting rules and procedures are described in sections [8.4.5](#) and [8.4.6](#).

7.2 PARTICIPANT DISCONTINUATION/WITHDRAWAL FROM THE STUDY

Participants are free to withdraw from participation in the study at any time upon request.

Criteria and procedures for withdrawal and replacement of a participant by the investigator are provided in section [8.4.3](#).

7.3 LOST TO FOLLOW-UP

A participant will be considered lost to follow-up if he or she fails to respond to the 1 week post-discharge phone and/or email contact. Study site staff will make at least 3 attempts to contact participants to complete this follow-up visit. These contact attempts should be documented in the participant's medical record or study file. Should the participant continue to be unreachable, they will be considered to have withdrawn from the study with a primary reason of lost to follow-up.

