
To assess potential effects of anxiety on the development of allergic reactions, and to support the psychological well-being of participants, each participant will complete standardized questionnaires assessing history of anxiety and past and current mental health within 30 days prior to or at Day 0. In addition, participants will have a mental health interview via a telehealth appointment before Day 0/admission to review questionnaire results and be offered strategies to

help manage distress. Vaccine-related anxiety will also be assessed at each timepoint, including before and after vaccine administration on Days 1 and 2. Responses will be assessed by a clinician, and a psychiatric evaluation and/or counseling or strategies to help with anxiety will be provided if indicated.

A member of the study team will perform videoconference, phone, and/or email follow-up with all participants within one week post-discharge to assess for any AEs from the study intervention. Participants will return to the NIH for follow-up visits approximately 1 and 5 months post-discharge to provide additional research samples, including samples to assess their response to the vaccine. At one of the follow-up visits (per investigator discretion), participants will undergo allergy skin testing to investigate the potential role of IgE in triggering allergic reactions to the vaccine. Mental health/anxiety questionnaires will be readministered at approximately day 30 and month 5, and anxiety levels will be assessed at each follow-up visit. Clinical follow-up will be provided as needed. At month 5, a brief questionnaire to garner participant feedback on the perceived benefits and burdens of the mental health assessments conducted on this study will also be administered. At the 5-month follow-up visit, we will offer participants the opportunity to receive a booster dose of the Pfizer-BioNTech vaccine if they did not have a severe allergic reaction when they received the second dose in the ICU (ie, those who had CoFAR grade 2 reaction or less will be eligible for the booster). For participants who decline the booster vaccination, the 5-month visit will be the final study visit.

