8.4.2 Documenting, Assessing, Recording, and Reporting Events

All AEs, including those that may appear to have a non-study cause (see “Causality” below), will be documented (e.g., on the clinical chart/progress notes/clinical laboratory record), recorded (e.g., research database), and reported (e.g., cumulatively from the research database, or according to protocol-specified expedited reporting mechanism) to the sponsor from the time informed consent is obtained through the timeframe specified below. At each contact with the subject, information regarding AEs will be elicited by open-ended questioning and examinations.

AEs and SAEs will generally be recorded, assessed, and reported according to the timeframes stated in the protocol and followed up as outlined in [Table 2](#). Descriptions of PSEEs and ESIs and timeframes for assessing and reporting these events are outlined in [Table 3](#) and [Table 4](#).

Table 2: Standard Times for Follow-up of Events

Event type	Follow events through
Related SAEs	End of subject participation in study, or if study personnel become aware thereafter
Unrelated SAEs	End of subject participation in study
Related non-serious AEs of grade 1 to 3	End of subject participation in study
All other related non-serious AEs	End of subject participation in study
Unrelated non-serious AEs	End of subject participation in study

Table 3: PSEE List and Reporting

Event description	How event will be reported
CoFAR Grade 1-3 allergic reaction	As an AE unless it meets statutory SAE criteria where it will be reported as an SAE. (All CoFAR Grade 4 events will be reported as SAEs.)

Table 4: ESI List and Reporting

Event description	How event will be reported

1. A single occurrence of an event that is uncommon and known to be strongly associated with vaccine exposure (e.g., Stevens-Johnson Syndrome, Guillain-Barré syndrome);
 
2. One or more occurrences of an event that is not commonly associated with vaccine exposure, but is otherwise uncommon in the population exposed to the drug (e.g., tendon rupture);
 
3. A single occurrence of myocarditis or pericarditis of any grade.
	
The ESI will be reported as an SAE/expeditedly even if it does NOT meet statutory SAE criteria.

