8.4.2.3.2 Serious Adverse Events (Expedited Reporting)

Unless otherwise specified above, all SAEs (regardless of relationship and whether or not they are also UPs) must be reported to the CSO as specified by the CSO (e.g., REDCap; use the Safety Expedited Report Form [SERF]/email if REDCap is not available). If the preferred/indicated mechanism for reporting is not available, the CSO/SMM should be contacted by telephone, fax, or other reasonable mechanism to avoid delays in reporting. ESIs will be reported in the same timeframe and mechanism as an SAE even though they do not meet the statutory SAE definition.

CSO CONTACT INFORMATION:

Clinical Safety Office
[name]
[name]
[contact]
[contact]
Email: [contact]
<https://crimsonredcap.cc.nih.gov/redcap/index.php>

Deaths and immediately life-threatening SAEs must be reported to the CSO promptly, and no later than the **first business day** following the day of study personnel awareness.

All other SAEs must be reported to the CSO no later than the **third business day** following the day of study personnel awareness.

If an individual subject experiences multiple SAEs in a closely timed/overlapping “cause-and-effect” (cascade) sequence, the principal investigator, after careful evaluation, will report ONLY primary/precipitating event(s) individually. SAEs that are determined to be definitely secondary to other SAEs will be detailed in the narrative portion of the report of the relevant primary/precipitating SAE. A clinical rationale and findings to support such reporting should be part of the narrative.

For each SAE report, the research database entry MUST match the corresponding entries on the SAE report (e.g., start and stop dates, event type, relationship, and grade), and **must be updated if necessary** (e.g., if the SAE report was generated after the corresponding AE was entered in the research database).

Unless otherwise specified above, SAEs that have not resolved by the end of the per-protocol follow-up period for the subject are to be followed until final outcome is known (to the degree permitted by the IRB-approved informed consent form). If it is not possible to obtain a final outcome for an SAE (e.g., the subject is lost to follow-up), and to update the CSO, the last known status and the reason a final outcome could not be obtained will be recorded by the investigator on an SAE report update and the CRF.

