9.4.4 Safety Analyses

The primary and secondary endpoints of this study are focused on safety and will be evaluated and analyzed as described above. Allergic reactions will be scored using the CoFAR Grading Scale for Systemic Allergic Reactions Version 3.0 and the Brighton Collaboration Criteria. Other

AEs following active vaccine administration are expected as described in Section 2.3.1, and will be assessed during the participant's ICU stay as well as the remote follow-up within 1 week post-discharge (Visit 2) and at the in-person follow-up visits (Visits 3, 4, and 6). Efforts will be made to record start and stop dates of all AEs (both allergic and nonallergic in nature), severity, relationship to the study intervention, and expectedness based on study intervention. If participants experience a CoFAR Grade 4 or higher reaction on Day 1, or any life-threatening adverse reaction related or unrelated to the study intervention, then no additional dosing will occur and participants will be followed per study protocol.

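### Section 7.3 withdraws a participant who cannot be reached at the week-1 contact from the whole study, giving up nearly five months of scheduled, retrievable safety and exploratory follow-up

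*Combined protocol and SAP*

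**What the plan says.** Loss to follow-up is defined only in Section 7.3, by a single trigger: "A participant will be considered lost to follow-up if he or she fails to respond to the 1 week post-discharge phone and/or email contact". It adds a condition, "Study site staff will make at least 3 attempts to contact participants to complete this follow-up visit", and requires the attempts to be documented. For someone who still cannot be reached, the consequence is that "they will be considered to have withdrawn from the study with a primary reason of lost to follow-up".

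The contact in question is Visit 2, a remote contact on Day 7 ± 2 (Section 1.2, Schema). Much of the schedule comes later. Section 4.1 says: "Participants will return to the NIH for follow-up visits approximately 1 and 5 months post-discharge to provide additional research samples". The Schema lists safety among the assessments at Visits 3, 4 and 6, and Section 9.4.4 plans AE assessment "at the in-person follow-up visits (Visits 3, 4, and 6").

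Three other provisions bear on what is lost:
- Table 2 (Section 8.4.2) follows related SAEs to "End of subject participation in study, or if study personnel become aware thereafter". Its other rows stop at the end of participation.
- Section 8.4.2.3.2 has unresolved SAEs followed to their final outcome where that can be obtained.
- Section 8.4.3.2 does not replace withdrawn participants, but keeps everyone exposed in the safety dataset.

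**The concern.** A missed telephone or email contact is normally handled as a missed visit. Here it ends participation, although the participant has not asked to leave and could still be reached for Day 30 or Month 5. Section 7.3 describes no way back. Section 8.4.3.1 allows re-enrolment only case by case, with written approval from the sponsor medical monitor.

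This sits awkwardly with the rest of the protocol. Under Sections 8.4.5 and 8.4.5.3, a participant whose study vaccinations are stopped after a serious reaction stays in follow-up.

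At stake is active late safety ascertainment, together with the 1- and 5-month antibody measurements, the skin test (Visit 3 or 4), the repeat mental-health questionnaires and any booster data. Timing adds to the concern: Section 2.3.1 places the raised myocarditis and pericarditis risk mainly in the first week after a second dose, just when the contact falls due. If silence were related to health, the people dropped would differ from those kept.

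**Working it through.** **Inputs**
- Visit 2: Day 5, 7 or 9 (Section 1.2, Day 7 ± 2).
- Last visit: Month 5 (Visit 4), or Month 6 (Visit 6) with booster (Section 1.2).
- Participant duration: about 5 or 6 months (Section 1.1).
- Reaction endpoints: 3 hours after the dose (Sections 1.1 and 3). Discharge: Day 3 unless a reaction needs more treatment (Section 4.1).
- Maximum N: 100 (Sections 4.1 and 9.2).
- Assumptions: 30.4 days per month; last visit on its nominal date; active ascertainment stops at Visit 2. Section 7.3 sets no date at which attempts stop, so any later cut-off shortens the loss day for day.
- Loss rate: not in the documents. A range of 0 to 20% is assumed for illustration only.

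**Step 1. Reproduce the stated duration.** 5 × 30.4 = 152 days and 6 × 30.4 = 182.4 days, matching the 5 or 6 months in the synopsis.

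**Step 2. Follow-up given up = last visit day − Visit 2 day.**

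| Visit 2 | To Visit 4 (152 days) | To Visit 6 (182.4 days) |
|---|---|---|
| Day 5 | 147.0 days, 4.84 months, 96.7% | 177.4 days, 5.84 months, 97.3% |
| Day 7 | 145.0 days, 4.77 months, 95.4% | 175.4 days, 5.77 months, 96.2% |
| Day 9 | 143.0 days, 4.70 months, 94.1% | 173.4 days, 5.70 months, 95.1% |

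The right-hand column applies only to someone who would have gone on to take the booster.

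**Step 3. Timing against the endpoints.** The primary and secondary endpoints are complete 3 hours after the relevant dose, during the inpatient stay. The Section 7.3 trigger comes after discharge, so it cannot affect them.

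**Step 4. Precision and bias for a late safety event.** With no events among n participants, the exact 95% upper bound is 1 − 0.025^(1/n). This reproduces the zero-event column of Table 5: 0.168 at n = 20, 0.045 at n = 80 and 0.036 at n = 100. Now suppose L of N participants are lost and no event is seen in the rest. The worst case counts every lost participant as an event and takes the Clopper-Pearson interval for L/N.

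| N | Lost (assumed) | Upper bound, 0/(N − L) | Worst case L/N, 95% CI |
|---|---|---|---|
| 100 | 0 | 3.6% | – |
| 100 | 5 | 3.8% | 1.6–11.3% |
| 100 | 10 | 4.0% | 4.9–17.6% |
| 100 | 20 | 4.5% | 12.7–29.2% |
| 20 | 0 | 16.8% | – |
| 20 | 1 | 17.6% | 0.1–24.9% |
| 20 | 2 | 18.5% | 1.2–31.7% |
| 20 | 4 | 20.6% | 5.7–43.7% |

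Lost precision is small. What matters is possible bias if loss is related to health. The last column is an outer bound, not a forecast.

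**Step 5. What survives.** Related SAEs that staff hear of later, SAEs already known and unresolved, and data collected up to Visit 2 are all kept. What goes is active questioning and examination at the later visits, and so any unreported event that only those visits would reveal.

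**The case against.** The case for leaving the rule alone has real substance.

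- **One unanswered call is not enough.** Three documented attempts are a minimum, and the participant must remain unreachable. This stands.
- **SAE follow-up does not simply end.** A reader might infer that withdrawal closes all AE and SAE follow-up. Table 2 and Section 8.4.2.3.2 do not support that: related SAEs learned of later are covered, and unresolved ones are pursued. Last known status is recorded only where no outcome can be obtained; the example given there is "If it is not possible to obtain a final outcome for an SAE (e.g., the subject is lost to follow-up"). These provisions nevertheless depend on the team knowing of the event or hearing about it.
- **Illness as the cause of silence is not shown.** A reader might infer that non-responders are mainly people who are ill. The documents give neither a loss rate nor reasons. The myocarditis timing makes the question reasonable but does not answer it. Against the inference, participants with symptoms after a visit are told to contact the team (Section 1.3, footnote b), and payment for Visits 1 and 2 follows Visit 2 (Section 5.7.2).
- **The main results are safe.** Step 3 confirms this.
- **Little may remain to protect.** As of September 15, 2022, only two participants had yet to complete the 5-month visit (Section 4.1). This limits the prospective effect, although the documents do not say how many were already withdrawn under the rule.
- **Later non-attendance is partly covered.** Section 8.4.3 allows withdrawal for non-compliance at the investigator's discretion. That is not a definition of loss at Visits 3, 4 or 6.

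None of this gives a reason to stop trying to reach a participant who has scheduled visits ahead.

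**Conclusion.** The point holds as a defect in an operative rule with limited reach. For each participant still unreachable after at least three attempts at Visit 2, Section 7.3 as written gives up 143 to 147 days of scheduled follow-up (4.7 to 4.8 of 5 months, 94 to 97%), or 173 to 177 days for a would-be booster recipient. The exposed data are late AEs and the antibody, skin-test, mental-health and booster results.

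The size per person rests on nominal visit dates and a cut-off at Visit 2. The size for the trial cannot be stated, because no loss rate is given; Step 4 shows only what assumed rates would mean. Health-related loss is plausible but not established. The primary and secondary reaction endpoints do not change, and at this version the remaining effect may be small.

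**What to change.** Reword Section 7.3 as follows:
1. A missed Visit 2, or Visit 5 for booster recipients, is a missed contact. The participant stays on study.
2. Staff try again for Visits 3 and 4, and Visit 6 where it applies.
3. Loss to follow-up is declared only when the participant cannot be reached through the close of the last applicable visit window.

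Item 3 also supplies the missing definition for someone who answers at Visit 2 and is lost later.

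An inquiry to the participant's health care provider is optional and should be made only with the participant's permission. Inclusion criterion 6 requires that a provider exist but does not authorise contact, and Section 10.3 restricts release of clinical information.

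The report should also state how many participants, if any, were already withdrawn under the present rule.

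The cost is one reworded paragraph and a few more contact attempts per non-responder, with no new visit or procedure. The 3-hour endpoint analyses need no change.
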